1 INTRODUCTION

This statistical analysis plan (SAP) describes the statistical analyses and data summaries to be performed to assess the efficacy, safety, and pharmacokinetics (PK) of rucaparib (CO-338) for Clovis Oncology, Inc sponsored clinical study CO-338-085, entitled “ATLAS: A Phase 2, Open-label Study of Rucaparib in Patients with Locally Advanced or Metastatic Urothelial Carcinoma.”

[figure not shown]
2 OVERALL STUDY DESIGN, OBJECTIVES, AND ENDPOINTS

2.1 Study Design

This clinical trial is a Phase 2 multicenter, open-label study evaluating rucaparib 600 mg twice daily (BID) for treatment of patients with recurrent locally advanced or metastatic urothelial carcinoma. This study will enroll patients with measurable disease per Response Evaluation Criteria in Solid Tumors (RECIST) Version 1.1 (v1.1). All patients must have received 1 or 2 prior standard of care treatment regimens and have radiologic progression during or after the most recent regimen. Patients who have received prior poly(adenosine diphosphate [ADP]-ribose) polymerase (PARP) inhibitor treatment will be excluded. Tumor tissue collected prior to rucaparib treatment will be analyzed to determine homologous recombination deficiency (HRD) status. This HRD status will be utilized to classify patients into molecularly-defined subgroups for efficacy analyses. The criteria used to determine if a patient is HRD-positive has been prospectively defined in this SAP (see [Section 3.2](#)).

The study schema is shown in [Figure 1](#). This study consists of a Screening Phase, a Treatment Phase, and a Post-treatment Phase. Patients will receive rucaparib monotherapy in the Treatment Phase, and will undergo procedures and assessments including regular safety and efficacy evaluations during the entire conduct of the study.

Figure 1. Study Schema

EOT = End of Treatment; PD = progressive disease
 * Tumor scans every 8 calendar weeks (±7 days) from Cycle 1 Day 1 up to 18 months then every 12 calendar weeks (±7 days) thereafter

2.2 Study Objectives and Endpoints

Table 1. Primary, Secondary, and Exploratory Objectives and Endpoints

Primary Objectives	Primary Endpoints
To evaluate objective response rate (ORR) in molecularly-defined homologous recombination deficiency (HRD)-positive and intent-to-treat (ITT) populations using a prospectively defined molecular signature.	ORR per Response Evaluation Criteria in Solid Tumor (RECIST) Version 1.1 (v1.1), as assessed by investigator, in HRD-positive and ITT populations
Secondary Objectives	Secondary Endpoints
To evaluate duration of response (DOR)	DOR per RECIST v1.1, as assessed by investigator
To estimate progression-free survival (PFS)	Disease progression according to RECIST v1.1, as assessed by the investigator, or death due to any cause
To estimate overall survival (OS)	OS
To evaluate safety and tolerability of rucaparib	Incidence of adverse events (AEs), clinical laboratory abnormalities, changes in ECGs and vital signs, and dose modifications
To evaluate steady-state pharmacokinetics (PK) of rucaparib	Trough (C_{min}) level rucaparib concentrations
Exploratory Objectives	Exploratory Endpoints
To assess biomarkers that correlate with response to rucaparib	Clinical efficacy of rucaparib in biomarker defined cohorts
To evaluate circulating cell-free tumor DNA (ctDNA) as a molecular marker of response to rucaparib	Association of cancer-related mutations detected in baseline ctDNA samples with response to rucaparib
To assess molecular changes over time in plasma and tumor samples	Association of changes in cancer-related mutations detected in plasma and tissue samples over time with response to rucaparib
To evaluate biomarkers associated with resistance to rucaparib	Biomarkers associated with resistance to rucaparib

2.3 Sample Size Justification

The overall sample size was determined by considering the number of patients needed for adequate safety and activity assessment of HRD-positive patients. Based on the estimated

prevalence of 60% HRD-positive patients in this population, approximately 200 patients will be enrolled into the study. This would result in enrollment of approximately 120 HRD-positive patients. The overall sample size will enable robust estimates of clinical activity in the HRD-positive and ITT populations.

3 GENERAL ANALYSIS CONVENTIONS

Quantitative variables will typically be summarized using frequencies and percentages for appropriate categorizations and may also be summarized using descriptive statistics. For variables summarized with descriptive statistics, the following will be presented: N, mean, standard deviation (StD), median, minimum, and maximum. Categorical variables will be presented using frequencies and percentages.

The Kaplan-Meier methodology will be used to summarize time-to-event variables.^{1,2} Estimates of the proportion surviving across time will be plotted, and if estimable, the 50th (median) percentile with the corresponding 95% confidence interval (CI) will be presented. The number of patients with events and the number of censored patients over time will also be displayed.

Baseline is defined as the last measurement on or prior to the first dose of rucaparib administration, unless otherwise specified.

All statistical analyses will be conducted with the SAS[®] System, Version 9.3 or higher.

3.1 Analysis Populations

The following analysis populations are defined for the study:

Safety Population – The safety population will include all patients who received at least 1 dose of rucaparib.

Intent-to-treat Population (ITT) – The ITT population will include all patients who received at least 1 dose of rucaparib.

HRD-positive Population – The HRD-positive population will include all patients who received at least 1 dose of rucaparib and are classified as HRD-positive by the prospectively-defined HRD signature (See [Section 3.2](#)).

3.2 Definition of HRD Signature

The HRD signature for this study is defined as the percentage of genome with loss of heterozygosity (LOH).³ Patients whose tumors have genome-wide LOH $\geq 10\%$ will be considered HRD-positive.

A mandatory tumor specimen is required for all patients; these tissue samples will be analyzed by Foundation Medicine, Inc. (FMI) using a next-generation sequencing (NGS) assay. This assay interrogates approximately 3,500 single-nucleotide polymorphisms (SNPs) across the genome and detects alterations in 310 genes.⁴ The SNPs on this panel will be used

to quantify the percentage of the genome with LOH, a marker of HRD shown to be associated with PARP inhibitor sensitivity in patients with relapsed ovarian cancer. This study will assess if LOH is correlated with PARP inhibitor sensitivity in patients with recurrent bladder cancer.

4 PATIENT DISPOSITION

Patient disposition will be summarized using frequency counts and the corresponding percentages. The number of patients in each analysis population, number of patients discontinued, and the primary reason for treatment discontinuation will be summarized.

5 PROTOCOL DEVIATIONS

The number of patients with major protocol deviations (eg, inclusion or exclusion criteria) will be determined prior to data base lock and will be summarized with frequencies and percentages or provided in a patient listing.

Protocol deviations will not be used to exclude any patients from the efficacy analyses.

6 DEMOGRAPHICS AND BASELINE CHARACTERISTICS

All demographic and baseline characteristics will be summarized for the safety, ITT, and HRD-positive populations.

6.1 Demographics

The demographic variables will be summarized with frequency tabulations and descriptive statistics. The demographic variables presented will include age, height, weight, gender, race, and region using the following categorizations:

- Age (years): ≤ 50 , 51-60, 61-70, 71-80, 81-90, > 90 ;
- Height (cm): ≤ 75 , $> 75-100$, $> 100-125$, $> 125-150$, $> 150-175$, > 175 ;
- Weight (kg): ≤ 50 , $> 50-75$, $> 75-100$, $> 100-125$, $> 125-150$, > 150 ;
- Race: American Indian or Alaska Native, Asian, Black, Native Hawaiian or Pacific Islander, White, Other, Not Reported
- Region: North America, Europe/Other

6.2 Baseline Clinical Characteristics

The following variables will be summarized with frequency tabulations:

- Histology (pure urothelial and mixed)
- De novo metastases (Y/N)
- Eastern Cooperative Oncology Group (ECOG) performance status (0, 1)
- Time since diagnosis of primary tumor (months) (0 to 12, > 12 to 24, > 24)

- Hemoglobin concentration (< 10 g/dL and ≥ 10 g/dL)
- Creatinine Clearance (CrCL) (< 60 mL/min and ≥ 60 mL/min)
- Metastatic sites (visceral, liver, lymph node only)
- Number of prior anti-cancer regimens (1, 2, >2)
- Prior platinum chemotherapy (Y/N)
- Type of prior platinum chemotherapy (cisplatin-based, carboplatin-based)
- Prior immune checkpoint inhibitor therapy (Y/N)
- Prior intravesical BCG (Y/N)
- Prior intravesical chemotherapy (Y/N)
- Prior neoadjuvant chemotherapy (Y/N)
- Prior adjuvant chemotherapy (Y/N)
- Prior radiotherapy (Y/N)
- Smoking status (current, former, never)
- Previous cystectomy/nephrourectomy: (Y/N)
- Number of Bellmunt risk factors (0, 1, 2, 3)

Descriptive statistics may also be used to summarize the continuous variables. Other baseline characteristic variables of interest may also be summarized if deemed appropriate.

6.3 Medical History

Medical history events will be classified using the Medical Dictionary for Regulatory Activities (MedDRA) classification system version 20.1 or more recent. Medical history data will be summarized using frequency tabulations by system organ class and preferred term.

7 STUDY DRUG EXPOSURE AND COMPLIANCE

The following variables will be summarized:

- Number of cycles initiated
- Duration of treatment (days, months)
- Dose intensity
- Number of dose reductions

Duration of treatment will be calculated as 1+ the number of days from study drug start date to date of study drug discontinuation. Dose intensity will be calculated as the actual dose received divided by the assigned dose amount. Descriptive statistics and frequencies/percentages for appropriate categorizations will be used to summarize study drug exposure variables.

8 PRIOR AND CONCOMITANT MEDICATIONS

All concomitant treatments documented during the study period will be summarized in frequency tabulations. Prior/concomitant medication coding will utilize World Health Organization (WHO) Drug version 2017MAR01DDE (Enhanced).

Separate data summaries of prior medications will be provided. Prior medications will be defined as those medications with both a start and a stop date that is before the day of the first dose of study drug administration. If either the start date and/or the stop date of the medication is missing so that it is unclear whether the medication was stopped prior to first dose of study drug administration then the medication will be included in the summary of the concomitant medications.

9 EFFICACY ANALYSIS

Efficacy analyses will be performed using the ITT and HRD-positive populations.

9.1 Primary Efficacy Analysis

The primary efficacy endpoint of ORR is defined as the proportion of patients with a confirmed response of complete response (CR) or partial response (PR) by RECIST v1.1 ([Appendix 1](#)) as assessed by the investigator. The ORR will be summarized with frequencies and percentages.

9.2 Secondary Efficacy Analyses

9.2.1 Duration of Confirmed Response

The duration of confirmed response is defined as the time from the date that a response is first documented per RECIST v1.1 by the investigator to the time that progression is first documented per RECIST v1.1 by the investigator, plus 1 day.

The duration of confirmed response will be analyzed and summarized in a Kaplan-Meier plot. Any patient with an ongoing response at the time of data cut-off for analysis will be censored at the date of the last post-baseline scan. In the case of a low censoring rate, the duration of response may be summarized with descriptive statistics.

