9.5.2 Secondary Efficacy Analyses

9.5.2.1 Duration of Response

Duration of confirmed response is defined as the time from the date that a response is first reported to the time that progression is first documented after the confirmed response.

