9.5.2.2 Progression-free Survival

Progression-free survival (PFS) will be calculated as 1+ the number of days from the first dose of rucaparib to disease progression or death due to any cause, whichever occurs first. Patients without a documented event of progression will be censored on the date of their last adequate tumor assessment (ie, radiologic assessment) or date of first dose of rucaparib if no post-baseline tumor assessments have been performed.

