If a complete response (CR) or partial response (PR) is noted, confirmatory scans should be performed at least 4 weeks after response was first documented.

Duration of Overall Response

The duration of overall response is measured from the time measurement criteria are met for CR or PR (whichever is first recorded) until the first date that recurrent or PD is objectively documented (taking as reference for PD the smallest measurements recorded since the treatment started).

The duration of overall CR is measured from the time measurement criteria are first met for CR until the first date that recurrent disease is objectively documented.

Duration of Stable Disease

Stable disease (SD) is measured from the start of the treatment until the criteria for progression are met, taking as reference the smallest measurements recorded since the treatment started.

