9.2.2 Progression-free Survival

Progression-free survival (PFS) is defined as the time from first dose of rucaparib to the date of first objective evidence of progression documented by the investigator per RECIST v1.1 or death due to any cause, whichever occurs first, plus 1 day. Patients without a documented event of progression will be censored on the date of their last adequate post-baseline tumor scan or date of first dose of study drug if no tumor scans have been performed. If a patient discontinues study drug due to something other than PD and subsequently begins another anti-cancer therapy (ACT) prior to a PFS, that patient will be censored at the last tumor scan prior to the start of ACT. However, PFS events occurring more than 90 days after discontinuation of study drug, but prior to start of subsequent ACT, will not be included in

the analysis and such patients will be censored at their last scan prior to the end of the 90-day window.

PFS will be summarized in a Kaplan-Meier plot; however in the case of a low censoring rate, it may be summarized with descriptive statistics.

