10 STATISTICAL / ANALYTICAL ISSUES

10.1 Handling of Dropouts or Missing Data

All data will be used to their maximum possible extent, but without any imputations for missing data. All time-to-event analyses will include censoring and the rules for deriving the censored values are described in more detail under each of the time-to-event endpoint descriptions.

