Progressive Disease	At least a 20% increase in the sum of the LD of target lesions, taking as reference the smallest sum on study (this includes the baseline sum if that is the smallest on study). In addition to the relative increase of 20%, the sum must also demonstrate an absolute increase of at least 5 mm. The appearance of one or more new lesions is also considered progression.

Abbreviations: LD = longest diameter; PD = progressive disease.

Evaluation of Nontarget Lesions	
Complete Response	Disappearance of all nontarget lesions and normalization of tumor marker level.
Stable Disease/Incomplete Response	Persistence of 1 or more nontarget lesion(s) or/and maintenance of tumor marker level above the normal limits.
Progressive Disease	Appearance of 1 or more new lesions and/or unequivocal progression of existing nontarget lesions.

If tumor markers are initially above the institutional ULN, they must normalize for a patient to be considered a complete responder.

Evaluation of Best Overall Response

The best overall response is the best response recorded from the start of the treatment until disease progression/recurrence (taking as reference for PD the smallest measurements recorded since the treatment started). The patient's best response assignment will depend on the achievement of both measurement and confirmation criteria.

Evaluation of Best Overall Response			
Target Lesions	Nontarget Lesions	New Lesions	Overall Response
CR	CR	No	CR
CR	Non-CR/non-PD	No	PR
CR	Not evaluated	No	PR

Evaluation of Best Overall Response				
Target Lesions		Nontarget Lesions	New Lesions	Overall Response
PR		Non-PD or not evaluated	No	PR
SD		Non-PD or not evaluated	No	SD
Not Evaluated		Non-PD	No	NE
PD		Any	Yes or No	PD
Any		PD	Yes or No	PD
Any		Any	Yes	PD
CR	=	complete response		
NE	=	not evaluable.		
PD	=	progressive disease		
PR	=	partial response		
SD	=	stable disease		

Patients with a global deterioration of health status requiring discontinuation of treatment without objective evidence of disease progression at that time should be classified as having symptomatic deterioration. Every effort should be made to document the objective progression, even after discontinuation of treatment.

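### Duration of response does not count death without documented progression as an event, and no censoring rule clearly covers it

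*SAP*

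**What the plan says.** **DOR.** SAP 9.2.1 starts the clock at the first documented response and runs it "to the time that progression is first documented per RECIST v1.1 by the investigator, plus 1 day". Protocol 9.5.2.1 runs it "to the time that progression is first documented after the confirmed response". The RECIST summary in Protocol Appendix 1 measures it "until the first date that recurrent or PD is objectively documented", and SAP Appendix 1 says the same. None of the four names death.

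**DOR censoring.** SAP 9.2.1 has one rule: "Any patient with an ongoing response at the time of data cut-off for analysis will be censored", at the last post-baseline scan. Protocol 9.5.2.1 has none. SAP 10.1 rules out imputation and says that "the rules for deriving the censored values are described in more detail under each of the time-to-event endpoint descriptions", which leads back to SAP 9.2.1.

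**PFS.** Protocol 9.5.2.2 counts days from first dose "to disease progression or death due to any cause, whichever occurs first". SAP 9.2.2 ends PFS at progression "or death due to any cause, whichever occurs first, plus 1 day". SAP 9.2.2 then leaves out PFS events more than 90 days after stopping study drug, and censors patients who start another anti-cancer therapy first.

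**Role of DOR.** It is a secondary endpoint (SAP Table 1), analysed in the ITT and HRD-positive populations (SAP 9). SAP 3 calls for a Kaplan-Meier median with 95% CI where estimable.

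**The concern.** In a single-arm trial with response rate as the primary endpoint, DOR tells the reader whether responses last. Under the plan as written, a patient whose response is cut short by death is not counted as having lost it. Nor does such a patient clearly fit a rule for responses ongoing at cut-off, so two programmers could produce different medians from the same data. If DOR is summarized descriptively, as the Protocol synopsis states and SAP 9.2.1 allows when censoring is low, the patient has no defined value at all.

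The case is foreseeable from the plan itself. Scans are 8 weeks apart, and 12 weeks apart after 18 months, so a death can fall between them. Treatment may stop for clinical progression (Protocol 10.1). SAP Appendix 1 provides for patients who stop because of declining health: those "without objective evidence of disease progression at that time should be classified as having symptomatic deterioration".

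**Working it through.** **1. The plan's own figures.** The documents give no planning figure for DOR. Their only power figure concerns response rate, and it reproduces. The smallest count with posterior Pr(p > 0.10) above 0.95 at N = 200 is 28. The exact type I error is then 0.0434 and the power at p = 0.20 is 0.989, against 0.043 and 0.989 in the fixed-design row of the operating-characteristics tables. No DOR quantity enters.

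**2. The definitions side by side, for a death without documented progression.**

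| Source | Is the death an event? | Rule if not |
|---|---|---|
| Protocol 9.5.2.1 (DOR) | No | None |
| SAP 9.2.1 (DOR) | No | Only for responses ongoing at cut-off |
| RECIST summaries, both documents | No | None |
| Protocol 9.5.2.2 (PFS) | Yes, by definition | – |
| SAP 9.2.2 (PFS) | Yes, unless more than 90 days after stopping drug or after new therapy starts | Last scan before the limit |

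Both PFS sections also say that patients lacking a documented progression event are censored. Read literally, that would censor deaths without progression and contradict the definition just before it.

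**3. Illustrative size.** Let λ be the hazard of documented progression after response and μ the hazard of death without it, both constant and independent. Let f = μ/(λ + μ) be the share of response-ending events that are such deaths. The documents do not give f, so it is assumed.

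- Median with death as an event: ln 2/(λ + μ)
- Median with death censored when it occurs: ln 2/λ
- Ratio: (λ + μ)/λ = 1/(1 − f)

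At f = 5, 10 and 20% the ratio is 1/0.95 = 1.05, 1/0.90 = 1.11 and 1/0.80 = 1.25.

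A simulation with 40 responders, an all-event median of 6.0 months and cut-off censoring uniform over 6 to 24 months (all assumed) agrees in direction and approximate size. With deaths censored, the typical median was 6.64 months at f = 10% and 7.50 at f = 20%. With deaths counted it was about 5.8.

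**4. Number of deaths implied, if every response has ended (responders × f).**

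| Responders | f = 5% | f = 10% | f = 20% |
|---|---|---|---|
| ITT, 200 × 20% = 40 | 2.0 | 4.0 | 8.0 |
| HRD-positive, 120 × 20% = 24 | 1.2 | 2.4 | 4.8 |
| ITT, 200 × 10% = 20 | 1.0 | 2.0 | 4.0 |
| HRD-positive, 120 × 10% = 12 | 0.6 | 1.2 | 2.4 |

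**5. Scale against sampling error.** With exponential durations and all responses ended, the standard error of the median divided by the median is about 1/(ln 2 × √n). That is 0.228 (n = 40), 0.294 (n = 24), 0.323 (n = 20) and 0.416 (n = 12). The largest gap above, 25% at f = 20%, is 0.250/0.228 = 1.1 standard errors with 40 responders and 0.250/0.294 = 0.85 with 24. This is for scale only, because the gap is a difference between definitions and not sampling noise.

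**6. Is the direction certain?** No. Step 3 censors at death, but the likely reading of SAP 9.2.1 censors at the last scan, which may be much earlier. Take seven responders: five progress at months 4, 6, 8, 10 and 12, and two have a last scan at month 3 and die at months 14 and 16.

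- Censored at last scan: the curve steps to 0.80, 0.60, 0.40, so the median is 8 months.
- Deaths as events: it steps to 0.857, 0.714, 0.571, 0.429, so the median is 10 months.

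Here censoring shortens the median.

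**The case against.** **Progression-only DOR is stated consistently, so it is a choice of estimand and not a contradiction.** This is partly right: the DOR texts agree with one another. But the choice is never stated as one, no rule says what happens to these patients, and the PFS definition shows that the authors name death where they intend it.

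**A reader might infer that every such death is a PFS event but not a DOR event.** The documents do not support that. SAP 9.2.2 excludes deaths more than 90 days after stopping drug or after new therapy, and patients who stop without objective progression are especially exposed to those limits. The contrast holds for the definitions, not for every patient.

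**A reader might infer that the reported DOR must be too long.** That is not supported either; step 6 is a counterexample. Lengthening is the usual direction, not a certainty.

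**The plan works to keep such deaths rare.** This stands. Scans continue after treatment stops for reasons other than progression, and the RECIST summaries ask sites to try to document objective progression even after stopping. That lowers f but does not supply a rule.

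**Simply adding death creates a new problem.** This also stands. Scans may stop once subsequent treatment starts, while survival follow-up continues (Protocol 7.5.3). Without a further rule, a late death on another drug would count as the end of a rucaparib response.

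**Conclusion.** The point holds as a gap in the definition and censoring of a secondary endpoint. A responder who dies without documented progression has no DOR event and no clearly stated censoring date. Treating such deaths as censored would usually lengthen the Kaplan-Meier DOR. The factors in step 3 rest on assumed shares, constant independent hazards and censoring at death, and they amount to about one standard error or less. The true size cannot be derived from the documents.

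A reader might go further and see a threat to the trial's main conclusion, or a demonstrated informative-censoring bias. Neither is supported. The response-rate test and the futility rules do not use DOR, DOR carries no hypothesis test, and the documents give no information on how deaths relate to later progression. Deaths are also reported separately through overall survival. The change is worth making because a reported median should have one definition, and the repair is cheap.

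**What to change.** In SAP 9.2.1 and Protocol 9.5.2.1:

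- Define DOR as the time from the first documented CR or PR that is later confirmed to documented progression or death from any cause, whichever is first, plus 1 day.
- Censor responders with neither event at the last adequate tumor scan. This also covers loss to follow-up.
- Censor responders who start subsequent anti-cancer therapy before an event at the last adequate scan before that therapy, as SAP 9.2.2 does for PFS.
- State that this definition governs over the RECIST summaries in the appendices.

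In both PFS sections, reword the censoring sentence so that it applies to patients with neither progression nor death. The DOR wording above has no 90-day window, and neither does Protocol 9.5.2.2. If the window stays in SAP PFS, say that the two endpoints differ for those late events.

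If progression-only DOR was intended, the minimum is to say so, give the censoring date for deaths, and add a sensitivity analysis that counts them.

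The cost is wording in two documents, best settled before database lock. Survival is already followed every 12 weeks (Protocol 7.5.3), so no new data are needed. The downside is that the reported DOR may be slightly shorter.
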